## 6.1.1 Primary Endpoints

### 6.1.1.1 Primary Analysis

#### Analysis Model

A stratified Cochran-Mantel-Haenszel (CMH) test will be used to compare the sPGA 0/1 response rates at Week 16 between BMS-986165 6 mg QD and placebo using the stratification factors from IRT specified in [Section 6.1](#). The odds ratio (ratio of odds in BMS-986165 6 mg QD group to the odds in the placebo group) and the corresponding 2-sided 95% CIs and p-values will be reported. Additionally, treatment differences in proportions and the 95% CI for the treatment difference will be provided. The common treatment difference in proportion with the confidence interval, common odds ratio with the confidence interval and p-value will be estimated by the Mantel-Haenszel method consistently.

A similar analysis will be performed to compare the PASI 75 response rates at Week 16 between BMS-986165 6mg QD and placebo.

Sponsor: Bristol-Myers Squibb  
Protocol no: IM011046

### Imputation Methodology

Non-responder imputation (NRI) will be used for coprimary efficacy endpoints for subjects who:

- Discontinue treatment or study prior to Week 16
- Have missing Week 16 endpoint data for any reason

NRI will be used as the primary method of imputation for the coprimary efficacy endpoints.

#### 6.1.1.2 Sensitivity Analyses

As a method to assess the sensitivity of the primary imputation method for the coprimary endpoints, further imputation methods will be used to impute Week 16 data in subjects who:

- Discontinue treatment or study prior to Week 16
- Have missing Week 16 endpoint data for any reason

The coprimary endpoints will be analyzed using the primary analysis method for each sensitivity imputation method described below:

##### Last Observation Carried Forward (LOCF)

The last observed post-baseline value will be carried forward and used as the Week 16 value. Subjects without a post-baseline will be considered a nonresponder.

##### LOCF and NRI

[figure not shown]
Subjects randomized to the placebo group will have the endpoint value imputed using LOCF (post-baseline). If a placebo subject does not have a post-baseline values, they will be considered a nonresponder. Subjects randomized to BMS-986165 6 mg QD will have their endpoint value imputed using the NRI methodology.

##### Tipping Point Analysis

Tipping point analysis will further be used to assess the robustness of the primary study results. Different number of events between treatment groups will be assessed until the study conclusion is changed. Each imputed value is initially imputed as a responder. The imputed values in the placebo group will remain as responders while the BMS-986165 imputed values are replaced as a nonresponders one at a time, therefore changing the number of events between groups. Once all imputed values in the BMS-986165 group have been replaced with nonresponders values, the data will reset to where the BMS-986165 group imputed values are all responders and one by one the imputed values in the placebo group are replaced with a nonresponder until all placebo are nonresponders and all BMS-986165 are responders. Furthermore, every pair of imputations between the placebo and BMS-986165 groups will be assessed similarly, creating a matrix of possible patterns.

At each iteration, the statistical analysis is assessed, and the direction of the analysis is recorded. A graph will be provided to identify at what point to which the difference in events cause a direction shift in study results. The tipping point analyses will be based on a two-sample chi-square test approach rather than a stratified CMH test approach for simplicity of the analysis.

Figure 1: Example of Tipping Point Analysis Direction Boundary

Sponsor: Bristol-Myers Squibb

Protocol no: IM011046

### “Responders” in missing BMS-986165 Group

[Figure 1](#) represents an example of the tipping-point analysis for all subjects with missing primary efficacy endpoint (responder/non-responder) in BMS-986165 group (N=5) and placebo group (n=5). Gray cells represent pairs where the statistical analysis resulted in non-significance. Green cells represent pairs where the statistical analysis resulted in significant difference between groups. The tipping-point boundary is where the green cells become gray.

#### Multiple Imputation

Multiple imputation (MI) will be used for sensitivity analyses for each of the coprimary efficacy endpoints, PASI 75 response at Week 16 and sPGA 0/1 response at Week 16. Multiple imputation of missing data for PASI 75 response and sPGA 0/1 response will be performed by fully conditional specification (FCS) using PROC MI in SAS with the FCS option. The FCS MI specifies the multivariate imputation model on a variable-by-variable basis by a set of conditional densities. For each missing value at Week X, the FCS MI will generate values from a conditional distribution for the missing data given the other data prior to Week X. The FCS MI model will include treatment group and stratification factors for randomization. A total of 1000 imputed (complete) datasets will be generated for the MI analysis. The same test procedure used for the main analysis (CMH test), will be used to analyze the responder endpoint from each imputed dataset. SAS PROC MIANALYZE will be used to pool the results from the CMH tests and generate an overall result by Rubin’s rules (1987).

#### 6.1.1.3 Supportive Analyses

##### Per Protocol Population Analysis

The coprimary endpoints will be analyzed using the PPS using the primary analysis methodology and primary imputation method.

## 6.1.2 Key Secondary Endpoints

### 6.1.2.1 Binary Endpoints

#### Analysis Model

CMH tests will be used to compare response rates between either BMS-986165 6mg QD and placebo or apremilast using the stratification factors from IRT specified in [Section 6.1](#). The odds ratio (ratio of odds in BMS-986165 6 mg QD group to the odds in the placebo or apremilast group) and the corresponding 2-sided 95% CIs and p-values will be reported. Additionally, treatment differences in proportions and the 95% CI for the treatment difference will be provided.

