### **4.2 Number of Subjects**

Approximately 600 qualified subjects will be randomized in a 2:1:1 ratio to BMS-986165 6 mg QD, apremilast 30 mg BID, and placebo, respectively. [REDACTED]

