### **2) Type of Subject and Target Disease Characteristics**

- a) Men and women diagnosed with stable plaque psoriasis for 6 months or more. Stable psoriasis is defined as no morphology changes or significant flares of disease activity in the opinion of the investigator
- b) Deemed by the investigator to be a candidate for phototherapy or systemic therapy
- c)  $\geq 10\%$  of BSA involvement at Screening Visit and Day 1
- d) Psoriasis Area and Severity Index (PASI) score  $\geq 12$  and static Physician's Global Assessment (sPGA)  $\geq 3$  at Screening Visit and Day 1

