## 2.5 Changes in Statistical Considerations from the Protocol

The following is a list of the important changes in the SAP from the Statistical Considerations section in the protocol:

- The hierarchical testing order for the key secondary endpoints has been updated and two separate hierarchies have been provided, one for US submission and one for ex-US submission (see [Tables 1](#) and [2](#) in Sec. 6.1.3). The update to the hierarchies are due to emerging information from clinical trials conducted with other agents recently approved for the treatment of psoriasis. The hierarchies presented in this document supersede the one that is in the protocol.

Sponsor: Bristol-Myers Squibb

Protocol no: IM011046

- Key secondary endpoints were added for the comparison of BMS-986165 to apremilast for sPGA 0/1, PASI 75, and PASI 90 at Week 24.
- Imputation methods were updated to remove the prohibited medication/therapy criteria for binary and continuous endpoints.
- The Full Analysis Set was changed from “all subjects who were randomized to receive assigned study treatment” in the protocol to “all subjects who are randomized”.
- The list of relevant protocol deviations provided in the protocol was updated for determination of the Per Protocol population.
- Logistic regression analyses for binary endpoints were removed as these are similar to the CMH analyses.

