### 6.1 Efficacy Analyses

All efficacy analyses will be performed using the FAS, unless otherwise specified.

Tests of significance of BMS-986165 6 mg QD vs. placebo for the coprimary endpoints will be two-sided with a significance level of 0.05. Both coprimary endpoints need to demonstrate statistical significance to result in a successful study.

The key secondary endpoints will be tested with a two-sided significance level of 0.025 to compare BMS-986165 6mg QD vs. placebo and vs. apremilast. A hierarchical testing approach will be used for testing of

Sponsor: Bristol-Myers Squibb

Protocol no: IM011046

key secondary endpoints (see [Section 6.1.3](#)). Two-sided 95% confidence intervals (CIs) will be provided for all efficacy estimates. [REDACTED]

Coprimary and key secondary efficacy endpoints will be displayed graphically by treatment group and visit, as applicable. All efficacy endpoints will be summarized descriptively.

Due to small sample sizes in China and Japan and differences in stratification factors, analyses will be stratified by a combination of the stratification factors used in randomization. The stratified levels are provided below:

- US/PRIOR USE/< 90 KG
- US/PRIOR USE/≥90 KG
- US/NAÏVE/<90 KG
- US/NAÏVE/≥90 KG
- ROW/PRIOR USE/< 90 KG
- ROW/PRIOR USE/≥90 KG
- ROW/NAÏVE/<90 KG
- ROW/NAÏVE/≥90 KG
- JAPAN/PRIOR USE
- JAPAN/NAÏVE
- CHINA/PRIOR USE
- CHINA/NAÏVE

If there is not at least one subject per treatment group in each of the China and Japan strata, then these regions will be collapsed together to form the following stratified levels for analyses:

- US/PRIOR USE/< 90 KG
- US/PRIOR USE/≥90 KG
- US/NAÏVE/<90 KG
- US/NAÏVE/≥90 KG
- ROW/PRIOR USE/< 90 KG
- ROW/PRIOR USE/≥90 KG
- ROW/NAÏVE/<90 KG
- ROW/NAÏVE/≥90 KG
- ASIA/PRIOR USE
- ASIA/NAÏVE

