### 6.1.2.2 Continuous Endpoints

#### Analysis Model

Analysis of covariance (ANCOVA) models will be used to compare the change between BMS-986165 6 mg QD and placebo or between BMS-986165 6 mg QD and apremilast at Week 16. Treatment group will be included in the model as well as the stratification factors from IRT specified in [Section 6.1](#) and will be considered as fixed effects. The baseline value will be added into the model as a covariate. The adjusted least-squares (LS) means as well as the treatment differences based on LS means and the corresponding 2-sided 95% CIs will be provided for the difference between BMS-986165 6 mg QD and placebo or apremilast.

[figure not shown]

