#### 8.2.1.1 static Physician's Global assessment (sPGA)

The sPGA is a 5-point scale of an average assessment of all psoriatic lesions based on erythema, scale, and induration. The sPGA measure determines psoriasis severity at a single point in time (without taking into account the baseline disease condition) as clear (0), almost clear (1), mild (2), moderate (3), or severe (4). A higher score equates to higher severity of disease.

The individual scores at each visit for erythema (E), induration (I) and scaling (S) will be captured via the eCOA system. Scores will range from 0 to 4. A total score will also be computed based on the average of the 3 characteristic scores.

$$\text{Total average score} = \frac{E + I + S}{3}$$

The total average score will be calculated in the eCOA system. The average score will be rounded to the nearest whole number. For example, if the total average score is ≤1.49 the score will be rounded to 1. If

Sponsor: Bristol-Myers Squibb

Protocol no: IM011046

the score is  $\geq 1.5$  the score will be rounded to 2. The primary endpoint is derived from the total average score.

sPGA 0 is derived as the binary indicator for sPGA from the calculation above equal to 0 or not;

sPGA 0/1 is derived as the binary indicator for sPGA from the calculation above equal is less than 2 or not;

All individual scores and total average score assessed at each week throughout the study will be transferred to PRA for analysis. The endpoint derivations will be performed in the analysis datasets.

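### The binary key secondary comparisons with apremilast leave out baseline severity, which the trial already collects; a pre-specified adjustment could add a small amount of power at no cost in patients

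*SAP*

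**What the plan says.** SAP 6.1.2.1 sets the test for the binary key secondary endpoints: "CMH tests will be used to compare response rates between either BMS-986165 6mg QD and placebo or apremilast using the stratification factors from IRT". SAP 6.1 defines the strata: "analyses will be stratified by a combination of the stratification factors used in randomization". This gives 12 levels of region, prior biologic use and body weight, or 10 if Japan and China are collapsed. Neither baseline sPGA nor baseline PASI is among them.

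Other parts of the plan bear on this:

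- **Continuous endpoints (SAP 6.1.2.2).** The ANCOVA does adjust: "The baseline value will be added into the model as a covariate".
- **Availability.** Protocol 5.1 makes PASI of at least 12 and sPGA of at least 3 entry criteria at both Screening and Day 1. SAP 8.1 allows a screening value if the Week 0 value is missing.
- **Existing use.** SAP 6.1.4 already splits the coprimary endpoints by baseline sPGA (3, 4) and PASI (up to 20, above 20).
- **Level.** SAP 6.1: "The key secondary endpoints will be tested with a two-sided significance level of 0.025". The protocol synopsis adds that, once a test fails, later p-values in that branch are descriptive.
- **Size.** Protocol 4.2: "Approximately 600 qualified subjects will be randomized in a 2:1:1 ratio to BMS-986165 6 mg QD, apremilast 30 mg BID, and placebo, respectively".
- **Logistic model.** SAP 2.5: "Logistic regression analyses for binary endpoints were removed as these are similar to the CMH analyses".

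**The concern.** A covariate that predicts the outcome and is measured before randomization can narrow the treatment contrast without adding a patient. SAP 8.2.1.1 describes the sPGA scale as assessed "without taking into account the baseline disease condition". The endpoint adds a 2-point improvement, but for an eligible subject that condition never binds. From baseline 3, a score of 1 is already a 2-point fall; from baseline 4 it is a 3-point fall. Likewise, sPGA 0 needs a fall of 3 or of 4. Baseline severity is therefore a natural candidate predictor for these endpoints.

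The comparison with placebo is not the issue: at the Phase 2 PASI 75 rates (68.9% v 6.7%) coprimary power is essentially 100%. The apremilast branch has about 300 v 150 subjects at two-sided 0.025, tested in sequence, so one narrow miss ends formal testing for everything below it.

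**Working it through.** **No figure to reproduce.** The visible text gives no apremilast response rate, target difference or power. What can be checked agrees: 600 at 2:1:1 is 300/150/150, and the two branch levels sum to 0.025 + 0.025 = 0.05. All rates and prognostic strengths below are assumptions, except 68.9% for BMS-986165, which is Phase 2 PASI 75 at Week 12 on 3 mg BID (Protocol 2.1).

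**Which endpoints are affected.** SAP 4.1.2.2 lists 12 binary endpoints against apremilast: 6 at Week 16, 3 at Week 24, and 3 at Weeks 52 and 24 jointly. Six are PASI 75 or PASI 90 (2 × 3 time points), already percent changes. The other six are thresholds: sPGA 0/1 three times, and sPGA 0, ss-PGA 0/1 and PSSD symptom score 0 once each.

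**Step 1: explained variance.** Let R² be the outcome variance explained by baseline beyond the strata. For baseline sPGA as 3 or 4, R² = q(1−q)g² / [p(1−p)], where q is the share at 4, g the gap in response rate and p the overall rate (0.5 here).

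- g = 10 points: 0.2 × 0.8 × 0.1² / 0.25 = 0.0064 at q = 20%, and 0.010 at q = 50%.
- g = 20 points: 0.026 at q = 20%, and 0.040 at q = 50%.

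**Step 2: precision.** The interval narrows by 1 − √(1−R²), equivalent to 450 × [1/(1−R²) − 1] extra subjects.

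| R² | Narrower by | Extra subjects |
|---|---|---|
| 0.01 | 0.5% | about 5 |
| 0.02 | 1.0% | about 9 |
| 0.05 | 2.5% | about 24 |
| 0.10 | 5.1% | 50 |

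**Step 3: power.** Power = Φ[(Δ − 2.241·SE₀)/SE₁], with SE₀ pooled, SE₁ unpooled and both multiplied by √(1−R²).

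Worked case, 60% v 45%, R² = 0:
- Pooled rate: (300 × 0.60 + 150 × 0.45)/450 = 0.55.
- SE₀ = √(0.2475 × 0.01) = 0.0497.
- SE₁ = √(0.24/300 + 0.2475/150) = 0.0495.
- (0.15 − 0.1115)/0.0495 = 0.778, so power is 0.782.

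| Assumed rates | R² = 0 | 0.02 | 0.05 | 0.10 |
|---|---|---|---|---|
| 60% v 45% | 0.782 | 0.791 | 0.804 | 0.827 |
| 68.9% v 53.9% | 0.808 | 0.816 | 0.829 | 0.850 |
| 68.9% v 48.9% | 0.969 | 0.972 | 0.976 | 0.982 |
| 20% v 10% | 0.688 | 0.698 | 0.714 | 0.742 |

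**Step 4: simulation of precision.** 1500 trials per case, 300 v 150, 10 strata, 55% v 40%. The standard error of the standardized risk difference, relative to the stratified Mantel-Haenszel one, was 0.999, 0.993, 0.981 and 0.950 for a covariate odds ratio per SD of 1.0, 1.25, 1.5 and 2.0. Rejection went from 0.796, 0.801, 0.785 and 0.803 with CMH to 0.801, 0.806, 0.813 and 0.835 with adjusted logistic regression. Monte Carlo error on each is about √(0.8 × 0.2/1500) = 0.010, though both tests use the same simulated data.

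**Step 5: the form of the test.** At 50% v 36% with 20% at baseline sPGA 4, a covariate-adjusted logistic score test raised power over CMH from 72.5% to 74.3% (odds ratio 0.5 for sPGA 4, 0.85 per SD of PASI) and from 72.8% to 75.9% (0.5 and 0.7). Under the null at 5 to 10% response it rejected 2.1 to 2.5% at nominal 2.5%. A Wald test on the standardized risk difference with influence-function variance rejected 3.2 to 3.6% across two simulations, against about 2 to 2.6% for CMH. At 36% response that Wald test was on target (2.5%). Adding baseline sPGA as a further CMH stratum changed information by only −2% to +4%. Adding both severity splits would make up to 12 × 2 × 2 = 48 strata.

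**The case against.** The strongest case against is that nothing here is wrong. CMH on the randomization factors is valid, agrees with Protocol 9.4.2 and already adjusts for three factors. A reader might infer more than the documents support, in four ways:

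- **That the binary endpoints ignore baseline.** PASI 75 and PASI 90 are defined against it, and so in wording is sPGA 0/1. The objection stands for PASI. For sPGA 0/1 it is formal only, because entry at 3 or above makes the 2-point condition automatic.
- **That precision is known to be lost.** No visible text links baseline severity to response, gives the share at sPGA 4, or gives an apremilast rate. This stands, and makes the gain conditional.
- **That dropping logistic regression removed the adjusted analysis.** Protocol 9.4.1.3 shows that model covered only the coprimary endpoints and held only treatment and stratification factors. Nor was it the only other binary model: SAP Appendix 2 lists a binary GEE against apremilast in Section 6.1.5.1, which is not visible, so its covariates cannot be checked.
- **That any adjusted test could replace CMH without risk.** The Wald form above exceeds its level at low response rates, and clearance endpoints such as sPGA 0 may have low rates. This stands and governs the choice of test.

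Power may also already be high. With the 0.5 and 0.85 odds ratios, a simulation gave 94.5% for CMH and 95.1% adjusted at 68.9% v 50%, and 99.6% v 99.7% at 68.9% v 45%. There the gain is negligible.

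**Conclusion.** The point holds as an optional efficiency gain. It does not show an error, a bias or a contradiction. The visible key secondary analyses against apremilast omit a covariate that is collected for essentially everyone, is plausibly prognostic for the threshold endpoints, and has its counterpart in the plan's own ANCOVA.

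The size depends on assumptions that the documents do not settle. If baseline is not prognostic, the gain is nil. Under assumed weak to moderate prognosis it is about 1 to 3 power points where power is near 73 to 75%. A 5% narrower interval needs a strong covariate (R² of 0.10, or an odds ratio of 2 per SD at 55% v 40%). At about 95% power or more, little changes. The 300 v 150 comparison is itself approximate: China has no apremilast arm, and SAP 6.6.1 excludes COVID-affected subjects from the Week 52 endpoints.

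**What to change.** Before unblinding, amend SAP 6.1.2.1 for the binary apremilast endpoints:

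1. **Test.** Pre-specify a covariate-adjusted test that holds its size at low response rates, for example a score test from a logistic model with treatment, the IRT strata and the baseline value of the relevant scale. Use sPGA and PASI for the sPGA and PASI endpoints, ss-PGA for ss-PGA 0/1, and the PSSD symptom score for PSSD symptom score 0.
2. **Estimate.** Report the marginal risk difference standardized over a stated population, with a small-sample-corrected robust variance. State how subjects from China are handled.
3. **Support.** Keep the stratified CMH as the supporting analysis.

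This needs no patients, visits or new data. The cost is SAP wording, added programming and reliance on a working model. SAP 7.2 keeps the codes blinded until database lock, so the choice can be fixed before any result is known.

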#### Imputation Methodology for Week 16 Endpoints

NRI will be used for key secondary efficacy endpoints for subjects who:

- Discontinue treatment or study prior to Week 16
- Have missing Week 16 endpoint data for any reason

#### Imputation Methodology for Week 24 Endpoints (for comparison of BMS-986165 6 mg QD to apremilast)

NRI will be used for key secondary efficacy endpoints for subjects who:

- Discontinue treatment or study prior to Week 24
- Have missing Week 24 endpoint data for any reason

#### Imputation Methodology for Week 52 Endpoints (for comparison of BMS-986165 6 mg QD to apremilast)

The key secondary endpoints included in this analysis are the following:

- sPGA 0/1 response with at least a 2-point improvement from baseline at Week 52 and at Week 24

Sponsor: Bristol-Myers Squibb

Protocol no: IM011046

- PASI 75 response at Week 52 and at Week 24
- PASI 90 response at Week 52 and at Week 24

Subjects must meet response criteria at both Weeks 24 and 52 in order to be considered a responder. Those who do not meet response criteria at both weeks will be considered a nonresponder. NRI will be used for the above key secondary endpoints for subjects who:

- Discontinue treatment or study prior to Week 52
- Have missing Week 52 or Week 24 endpoint data
- Switch from apremilast to BMS-986165 at Week 24 for Week 24 PASI 50 nonresponders

### 6.1.2.2 Continuous Endpoints

#### Analysis Model

Analysis of covariance (ANCOVA) models will be used to compare the change between BMS-986165 6 mg QD and placebo or between BMS-986165 6 mg QD and apremilast at Week 16. Treatment group will be included in the model as well as the stratification factors from IRT specified in [Section 6.1](#) and will be considered as fixed effects. The baseline value will be added into the model as a covariate. The adjusted least-squares (LS) means as well as the treatment differences based on LS means and the corresponding 2-sided 95% CIs will be provided for the difference between BMS-986165 6 mg QD and placebo or apremilast.

[figure not shown]
#### Imputation Methodology for Week 16 Endpoints

For continuous key secondary endpoints, a modified baseline observation carried forward (mBOCF) approach will be used for missing data. The baseline observation will be carried forward for subjects who discontinue study treatment prior to Week 16 due to:

- Lack of efficacy
- AEs

[figure not shown]
Subjects who discontinue study treatment prior to Week 16 for other reasons or who have a missing Week 16 value will have the last valid observation carried forward (including the baseline value as applicable).

[figure not shown]
Subjects with a missing baseline value will be excluded from the analysis for the change from baseline endpoint.

Sponsor: Bristol-Myers Squibb  
Protocol no: IM011046

---

[figure not shown]

[figure not shown]
